# 1.4 Rationale for conducting this study

The frequency of HRD in prostate cancer increases substantially from the population of patients with localized prostate cancer to those with metastatic disease, reflecting the lethal phenotype mediated by HRD. Lethality is a reflection of early micrometastatic dissemination and an inability of local therapy alone to cure the disease. Men with localized prostate cancer with HRD either as a result of germline or somatic inactivation require better systemic therapy to improve their outcomes. The primary objective of this study is to assess whether the use of the PARP inhibitor olaparib prior to prostatectomy will result in pCR, which is credentialed in other malignancies as a surrogate for effective systemic elimination of tumor and long term cure. This is a pilot study to assess the feasibility of this approach in men with localized disease, with assessment of pCR, surgical margin status, extracapsular extension, seminal vesicle and nodal involvement, all of which are pathologic indicators of activity of neoadjuvant therapy. It is anticipated that the majority of patients will be known to be carriers of pathogenic germline variants, although a subset with purely somatic inactivation and HRD may identified in other ways. There is no evidence that tumors with germline vs. somatic inactivation will be differentially sensitive to PARP inhibition, so both populations will be eligible. A neoadjuvant PARP inhibitor study has not been performed in patients with prostate cancer and this study will also assess the safety and toxicity of olaparib in this patient population. If neoadjuvant therapy does not result in pCR, the remaining tissue is by definition resistant to therapy and remaining tumor tissue will be interrogated for mechanisms of resistance to inform future combination studies in advanced and localized HRD prostate cancer.

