## 1.5 Benefit/risk and ethical assessment

The risk/benefit associated with the use of olaparib administered prior to prostatectomy must weigh the risks of the drug, both acute and long term, vs. potential benefits. The justification for adding systemic therapy for patients with HRD prostate cancer is related to the significantly increased risk of relapse and death associated with HRD. Patients who are BRCA2 carriers have a 4-5 fold increased risk of developing prostate cancer . Once germline carriers are diagnosed with prostate cancer, their crude risk of metastasis and cancer specific mortality is increased approximately 8 fold . Although in multivariate analysis the overall risk of cancer specific mortality decreases, the presence of a germline mutation significantly increases the risk of being diagnosed with high risk or metastatic disease reflecting an aggressive biology . The frequency of other germline DNA repair genes is so low in the general population of men diagnosed with localized disease that no studies of their impact on relapse and cancer specific mortality has been carried out. Given the rarity of these variants in localized disease and the increased incidence in patients with metastatic disease. we anticipate that a similar increase in mortality attends the presence of these mutants . As noted, cancer specific relapse and death after definitive therapy is essentially always related to regional nodal or systemic metastasis, which can only be addressed with better systemic treatment. The relative risk/benefit calculation for treatment men with localized HRD prostate cancer with olaparib must balance risks of morbidity and mortality of the disease with toxicities of the therapy. The risks of cancer related morbidity and mortality are outlined above. The risks of olaparib outlined in section 1.2.2 and 1.2.3 are primarily myelosuppression, which in patients with advanced prostate cancer not receiving concurrent therapy was grades 1 or 2 and nausea and vomiting grades 1 or  $2^{20}$ . In other settings the frequency of more significant toxicities, including pneumonitis, myelodysplasia and leukemia are rare (Section 1.2) and MDS/leukemia frequency is confounded by prior therapy for the majority of patients (ovarian cancer) with the DNA damaging agent platinum, and known to cause MDS/AML at a very similar frequency in this patient population . There is no evidence from neoadjuvant studies of PARPi in patients with breast cancer that PARPi increases the risk of perioperative complications . The use of prostatectomy in this study as definitive therapy is appropriate as there is clear evidence that radiation and prostatectomy are at least equivalent with some studies suggesting better outcomes in high risk patients . The potential benefits of neoadjuvant PARPi for patients with HRD tumors could be reduced risk of relapse, metastasis or death which is significant in this patient population. This study will not formally evaluate long term outcomes but will provide pilot data regarding frequency of pCR, and improvement of other pathologic criteria which are predictive of relapse, as well as providing tissues which will allow interrogation of mechanisms of resistance if olaparib does not improve pCR rate.

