Starting on Day 1, all patients will ingest olaparib (300 mg twice daily) at the same times each day, without breaks (except as outlined for toxicity), for 90 days. The 90 day duration is chosen as a duration adequate to assess impact of neoadjuvant therapy on downstaging but not so prolonged that if patients do not respond to therapy, that potentially curative local therapy is being significantly delayed. Multiple studies have demonstrated in unselected populations that 90 day delay to surgery is not associated with any change in long term outcomes . During neoadjuvant therapy, dose reduction of olaparib is allowed for toxicity as detailed in the protocol. Patients should receive olaparib until 1 day prior to prostatectomy, until the

patient can no longer tolerate the treatment due to an adverse event, until the patient initiates another systemic antineoplastic drug or an investigational drug, or at the discretion of the Investigator. Safety and tolerability will be documented throughout the study and 30 days after prostatectomy by assessment of adverse events, vital signs, and laboratory assessments as defined in the Schedule of Activities. All adverse events will be monitored and recorded until the Safety Follow-up visit. Adverse events will be graded according to the National Cancer Institute Common Terminology Criteria for Adverse Events, Version 4.03 (NCI-CTCAE v4.03). In the event a patient discontinues olaparib due to a related adverse event, follow up will continue until adequate resolution of the adverse event, the physician deems the adverse event to be stable, the patient initiates another systemic antineoplastic drug or an investigational drug, or the patient withdraws consent from the study. A safety follow-up visit will be conducted approximately 30 days after the last dose of olaparib or before the initiation of a new systemic antineoplastic therapy or investigational agent, whichever occurs first. Any ongoing adverse event thought to be related to study treatment will be followed until the event has resolved to baseline grade, the event is assessed by the Investigator as stable, the patient initiates another systemic antineoplastic drug or an investigational drug, the patient is lost to follow-up, the patient withdraws consent, or it has been determined that study treatment or participation is not the cause of the adverse event.

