## 9.2 Monitoring of the study

Trial monitoring will be in accordance with the Fred Hutchinson Cancer Research Center (FHCRC)/University of Washington (UW) Cancer Consortium Institutional Data and Safety Monitoring Plan. Under the provisions of this plan, FHCRC Clinical Research Support coordinates data and compliance monitoring conducted by consultants, contract research organizations, or FHCRC employees unaffiliated with the conduct of the study. Independent monitoring visits occur at specified intervals determined by the assessed risk level of the study and the findings of previous visits per the institutional DSMP.

In addition, protocols are reviewed at least annually and as needed by the Consortium Data and Safety Monitoring Committee (DSMC), FHCRC Scientific Review Committee (SRC) and the FHCRC/University of Washington Cancer Consortium Institutional Review Board (IRB). The review committees evaluate accrual, adverse events, stopping rules, and adherence to the applicable data and safety monitoring plan for studies actively enrolling or treating patients. The IRB reviews the study progress and safety information to assess continued acceptability of the risk-benefit ratio for human subjects. Approval of committees as applicable is necessary to continue the study.

The trial will comply with the standard guidelines set forth by these regulatory committees and other institutional, state and federal guidelines.

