## 11.2 Determination of sample size

This is a pilot study assessing whether PARP inhibition with olaparib has the capacity to induce high pathologic complete respone (pCR) rates in men with tumors harboring DNA repair deficiencies (i.e. induce synthetic lethality). The primary efficacy endpoint will be the pCR rate as determined on prostatectomy specimens following 12-weeks of neoadjuvant olaparib. The historical complete response rate to 3-8 months of androgen deprivation with LHRH agonist and androgen receptor antagonist is  $\sim 10\%$  (H0). We anticipate a complete response rate of  $\geq 40\%$  (H1) following 12-weeks of olaparib in patients with homologous DNA repair deficient tumors (truncal mutations/copy loss). Therefore, a sample size of 15 patients would yield 80% power to detect a difference between the null and alternative pathologic complete response rates at a two-sided alpha = 0.05

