## 11.3 Methods of statistical analysis

Statistical analyses will be performed using all patients with evaluable data (e.g., pathologic staging among those who had a prostatectomy, and safety data among those who receive a dose of olaparib).

For efficacy analysis pathologic complete response is defined as the absence of morphologically identifiable carcinoma in the prostatectomy specimen, as evaluated by the site pathologist using standard methods. Formalin-fixed, paraffin-embedded slides will be evaluated by a central pathology review at completion of the study. Comparison of the actual pathologic complete response rate with the historial rate of 10%.

For safety analyses, all patients who received at least one dose of study drug and had at least one post-baseline safety assessment will be evaluated. Data will be descriptive, describing frequency of grade 1-5 adverse events. Data from all cycles of treatment will be combined in the presentation of safety data. AE will be listed individually by subject. The number of subjects experiencing each AE will be summarized by the Medical Dictionary for Regulatory Activities (MedDRA) system organ class, MedDRA preferred term and CTCAE grade. The number and percentage of subjects with adverse events in different categories (e.g. causally related, CTCAE grade ≥3 etc.) will be summarized. Any AE occurring before the first dose of investigational product (i.e. before study Day 1) will be included in the data listings but will not be included in the summary tables of adverse events. Any AE occurring within the defined 90 day follow-up period after discontinuation of olaparib will be included in the AE summaries. Hematology, clinical chemistry, vital signs, ECG data, demographic data, medical histories and concomitant medications will be listed individually by subject. For all laboratory variables, which are included in the current version of CTCAE, the CTCAE grade will be calculated. Summary statistics of mean, median, standard deviation, minimum, maximum and number of observations will be used. Details of any deaths will be listed for all subjects.

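### Section 9.2 refers to stopping rules, but the protocol supplies no trial-level rule, and the single-stage design of 15 men takes no early look at pCR

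*Combined protocol and SAP*

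**What the plan says.** - **Monitoring (section 9.2).** "The review committees evaluate accrual, adverse events, stopping rules, and adherence to the applicable data and safety monitoring plan". Review is at least annual and as needed, the IRB considers study progress and whether risk-benefit remains acceptable, and committee approval is needed to continue. No criterion is given.
- **Design (section 11.2).** "a sample size of 15 patients would yield 80% power to detect a difference between the null and alternative pathologic complete response rates". The null rate is about 10% and the alternative is 40% or more, at a two-sided alpha of 0.05. Sections 11.1 to 11.3 contain no interim analysis, no futility boundary and no trial-level toxicity boundary. The rules on interruption, discontinuation and proceeding to surgery (sections 5.4.10 to 5.4.12, 5.7 and 5.7.1) apply to individual patients.
- **Setting (section 1.4).** "A neoadjuvant PARP inhibitor study has not been performed in patients with prostate cancer".
- **Delay (section 3.2).** The 90 days is meant to be long enough to judge the treatment's effect "but not so prolonged that if patients do not respond to therapy, that potentially curative local therapy is being significantly delayed". The studies cited as showing no long-term effect of such a delay are described there as being in unselected populations.
- **Benefit and risk (section 1.5).** "The relative risk/benefit calculation for treatment men with localized HRD prostate cancer with olaparib must balance risks of morbidity and mortality of the disease" against the toxicity of treatment. The section describes these men as having a markedly raised risk of relapse and death. It does not discuss the surgical delay.
- **Timing.** Surgery is at day 90 ± 14 (section 5.4.4). Accrual is projected at 36 months (section 9.4). The site pathologist determines pCR, and central review takes place only when the study is complete (section 11.3).

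**The concern.** Each man's pCR status is known about three months after he starts, while accrual is spread over three years. Evidence that olaparib produces little or no pCR could therefore be in hand well before the trial is full. The plan as written makes no use of it: a run of specimens with residual tumour would leave enrolment open.

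If the drug does not produce pCR, later men accept the wait for surgery and the toxicity after the trial's main hypothesis has already weakened. Replacement (sections 5.4.6, 5.8 and 11.1.1) means that more than 15 men could be treated. The committees could act, but without a pre-set criterion an early closure would be ad hoc, and its effect on the final comparison with 10% would not have been worked out in advance.

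**Working it through.** **Inputs.** N = 15, H0 = 10%, H1 = 40%, two-sided alpha 0.05 (section 11.2); pCR of 1% or less without intervention (section 3.2, primary variable); 3% as the lower end of the historical range under androgen deprivation (section 1.1); accrual over 36 months (section 9.4).

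**1. The plan's own figure.** Section 11.3 compares the observed rate with 10% but names no test or cut-off. I assume an exact one-sample binomial test.
- Success at 4 or more of 15: P(X ≥ 4 | 15, 0.10) = 0.0556, above the upper-tail limit of 0.025.
- Success at 5 or more of 15: P(X ≥ 5 | 15, 0.10) = 0.0127, and power P(X ≥ 5 | 15, 0.40) = 0.7827.

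The stated 80% is reproduced, to rounding, as a fixed design with no interim look.

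**2. Probability of closing at 0 of 7,** (1 − p)^7:
- p = 1%: 0.99^7 = 0.932
- p = 3%: 0.97^7 = 0.808
- p = 10%: 0.90^7 = 0.478
- p = 40%: 0.60^7 = 0.028

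**3. Effect on power and alpha.** A stop costs a success only if a trial with 0 of 7 would have had at least 5 pCRs in the remaining 8.
- At 40%: P(X ≥ 5 | 8, 0.40) = 0.174. Loss = 0.028 × 0.174 = 0.0049. Power = 0.7827 − 0.0049 = 0.778.
- At 10%: P(X ≥ 5 | 8, 0.10) = 0.0004. Loss = 0.478 × 0.0004 = 0.0002. Upper-tail alpha = 0.0127 − 0.0002 = 0.0125.

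**4. Men spared.**
- Uniform accrual (an assumption): 36 / 15 = 2.4 months per man.
- Waiting 3 to 4 months for the seventh result: 3 / 2.4 = 1.25 to 4 / 2.4 = 1.67, so 1 to 2 more men start.
- Eight places remain after the seventh man, so a stop spares 8 − 2 = 6 to 8 − 1 = 7 men.
- Average saving at 10%: 0.478 × 6.5 = 3.1 men.
- Expected N under H0 if nobody starts during the wait: 7 + (1 − 0.478) × 8 = 11.2. Allowing for the wait, it is about 15 − 3.1 = 11.9.

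**5. Other looks, for comparison** (N = 15, success at 5 or more; expected N ignores the wait):

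| Close if | Stop at 10% | Stop at 40% | Power | Expected N at 10% |
|---|---|---|---|---|
| no look | – | – | 78.3% | 15 |
| 0 of 7 | 47.8% | 2.8% | 77.8% | 11.2 |
| 0 of 8 | 43.0% | 1.7% | 78.1% | 12.0 |
| 1 or fewer of 9 | 77.5% | 7.1% | 77.2% | 10.4 |

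The low cost does not depend on choosing exactly 7: the power loss in these examples is 0.2 to 1.1 percentage points.

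**The case against.** **The monitoring text is general.** Section 9.2 reads as standard institutional wording, and the institutional monitoring plan it invokes is not part of the documents. A reader might infer that the trial depends on a rule that was left out, or that all 15 men must be treated whatever happens. The documents support neither. That plan may hold criteria that cannot be seen here, and annual review over 36 months gives about three points at which continuation can be refused. What stands is that the protocol itself supplies no criterion and that early pCR is not a listed review item.

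**pCR is not the only benefit considered.** A reader might infer that the case in section 1.5 collapses without pCR. It does not: that section also counts improvement in other pathologic features and tissue for resistance work if pCR does not improve. Closing on pCR alone could end a trial that shows downstaging short of pCR. This stands as a cost of the rule.

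**The delay is addressed.** Section 3.2 says that 90 days was chosen to avoid significant delay, and it cites supporting studies. The documents do not show that the delay is harmful. What remains is that the evidence comes from unselected men, whereas section 1.5 describes this population as being at higher risk.

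**A single stage is legitimate in a 15-man pilot.** So it is. At the 10% null the look also fails to stop 52% of the time (1 − 0.478). The argument is that the look costs little, not that the existing design is invalid.

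**Conclusion.** The point holds as a design gap. The protocol refers to stopping rules without supplying a trial-level one, and its single-stage design takes no early look, in an untested setting where surgery waits about 90 days. A look at 7 men would cost about 0.5 percentage points of power and leave type I error slightly lower.

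The gain depends on the true rate. It is large if the drug is nearly inactive (93% chance of stopping at 1%) and moderate at the plan's null (48%, about 3 men spared on average). The 6 to 7 men spared is conditional on stopping. These figures assume an exact test with success at 5 or more of 15, uniform accrual, and a wait of 3 to 4 months for the seventh result.

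It would be wrong to read this as an error in the sample size: the 80% figure is reproduced.

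**What to change.** Add to section 11.2, with a cross-reference in section 9.2, a futility look that governs enrolment only. After the first 7 men in the primary efficacy analysis set, judged by the site pathologist's read, enrolment closes if none has pCR. Accrual is not paused for the look, and men already on treatment continue under the existing sections.

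State the operating characteristics with success at 5 or more of 15: stopping probability 48% at 10%, 2.8% at 40% and 93% at 1%; power 77.8% instead of 78.3%; upper-tail alpha 0.0125 instead of 0.0127; expected N 11.2 under H0 if no men start during the wait.

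Two definitions must be settled for the rule to work:
- **Which men count.** Section 11.1.1 requires the complete planned cycle, section 5.8 replaces men unable to receive more than 6 weeks, and section 11.3 uses all men with evaluable data.
- **How the site reads pCR.** Section 10.1 bases pCR on light microscopy without immunohistochemistry, but also asks for immunostaining of atypical foci.

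The text should name these downsides: about 0.5 points of power, a 2.8% chance of a wrong stop at 40%, fewer residual specimens for resistance work, and less precise secondary pathologic endpoints, including any downstaging short of pCR.

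The cost is a short amendment plus those two clarifications. The look does not provide a toxicity boundary; if the committees take one from the institutional plan, section 9.2 should say so. If the sponsor prefers no futility rule, section 11.2 should say that and give the reason.

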## 1.5 Benefit/risk and ethical assessment

The risk/benefit associated with the use of olaparib administered prior to prostatectomy must weigh the risks of the drug, both acute and long term, vs. potential benefits. The justification for adding systemic therapy for patients with HRD prostate cancer is related to the significantly increased risk of relapse and death associated with HRD. Patients who are BRCA2 carriers have a 4-5 fold increased risk of developing prostate cancer . Once germline carriers are diagnosed with prostate cancer, their crude risk of metastasis and cancer specific mortality is increased approximately 8 fold . Although in multivariate analysis the overall risk of cancer specific mortality decreases, the presence of a germline mutation significantly increases the risk of being diagnosed with high risk or metastatic disease reflecting an aggressive biology . The frequency of other germline DNA repair genes is so low in the general population of men diagnosed with localized disease that no studies of their impact on relapse and cancer specific mortality has been carried out. Given the rarity of these variants in localized disease and the increased incidence in patients with metastatic disease. we anticipate that a similar increase in mortality attends the presence of these mutants . As noted, cancer specific relapse and death after definitive therapy is essentially always related to regional nodal or systemic metastasis, which can only be addressed with better systemic treatment. The relative risk/benefit calculation for treatment men with localized HRD prostate cancer with olaparib must balance risks of morbidity and mortality of the disease with toxicities of the therapy. The risks of cancer related morbidity and mortality are outlined above. The risks of olaparib outlined in section 1.2.2 and 1.2.3 are primarily myelosuppression, which in patients with advanced prostate cancer not receiving concurrent therapy was grades 1 or 2 and nausea and vomiting grades 1 or  $2^{20}$ . In other settings the frequency of more significant toxicities, including pneumonitis, myelodysplasia and leukemia are rare (Section 1.2) and MDS/leukemia frequency is confounded by prior therapy for the majority of patients (ovarian cancer) with the DNA damaging agent platinum, and known to cause MDS/AML at a very similar frequency in this patient population . There is no evidence from neoadjuvant studies of PARPi in patients with breast cancer that PARPi increases the risk of perioperative complications . The use of prostatectomy in this study as definitive therapy is appropriate as there is clear evidence that radiation and prostatectomy are at least equivalent with some studies suggesting better outcomes in high risk patients . The potential benefits of neoadjuvant PARPi for patients with HRD tumors could be reduced risk of relapse, metastasis or death which is significant in this patient population. This study will not formally evaluate long term outcomes but will provide pilot data regarding frequency of pCR, and improvement of other pathologic criteria which are predictive of relapse, as well as providing tissues which will allow interrogation of mechanisms of resistance if olaparib does not improve pCR rate.
